Subsequently, marHRME will be performed of all Lugol's unstained (abnormal) sites prior to tissue biopsy. The endoscopist will activate the marHRME glasses and marHRME performed: (1) 1-10 ml proflavine hemisulfate (0.01%) will be sprayed on the esophageal mucosa, (2) the marHRME probe placed gently on the Lugol's abnormal areas, (3) the 'optical biopsy' image will be displayed on the AR glasses (endoscopic image will remain displayed on the standard monitor behind it). (Proflavine is used under an IND #102217).

The endoscopist will FIRST make a subjective interpretation ('non-neoplastic' vs. 'neoplastic'), record their confidence level in the diagnosis (high confidence vs. low confidence), and indicate their plan of action (a. biopsy, b. no biopsy, c. treat). All of this will be done WITHOUT the image-analysis software.

Once this qualitative read is recorded, the image analysis software will be turned on (foot pedal) and the software diagnosis provided in real-time with display on the AR glasses. The quantitative ("Machine") read will be recorded, the confidence level of the endoscopist obtained again, and the (revised) plan of action recorded (a numerical score). The software output (score) will be determined neoplastic (cancer) or non-neoplastic (normal) based on a predetermined

algorithm threshold. This quantitative read may influence clinician read, plan, and confidence.

The HRME procedure (including "man" and "machine" reads), standard endoscopy and biopsy time will be recorded. The research coordinators will indicate the biopsy number/location on an esophageal map diagram. The biopsies from each site will be placed in formalin per standard-of-care and labeled according to biopsy location (quadrant: 12, 3, 6, 9 o'clock).

In all subjects, all Lugol's abnormal areas will be biopsied (to uphold the standard of care); however, HRME "non-neoplastic" sites will be considered not tissue-biopsied for purpose of the analysis. All biopsies will be submitted for consensus diagnosis by an expert GI pathologist. All patient adverse events (bleeding, infection, perforation) that occur within 7 days after the procedure will be recorded on follow up call.

It is very possible that the HRME will increase the accuracy of standard Lugol's screening and may reduce unnecessary biopsies by improving specificity. With novices, the HRME + computer algorithms may be very likely to improve accuracy and performance, based on our preliminary data from China.

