Many side effects go away soon after the procedure, but in some cases, side effects may be serious, long-lasting or permanent, and may even cause death. It is important that the participant tell the study staff about any side effects that he/she may have had even if he/she does not think it is related to the procedure. Allergic reaction (anaphylaxis) There is the possibility of a severe allergic reaction to the Proflavine contrast dye in which participant may have difficulty breathing and the blood pressure may drop. There are procedures in place to treat participant in endoscopy room in the event that this happens. Specimen Imaging Probe There are no known risks from the use of the imaging probe. Anesthesia There may be additional risks from the added time of additional sedation, such as decreased blood pressure. Aspiration (inhaling) of fluid into the lungs during endoscopy This might cause inflammation in the lungs. Safeguards to prevent this from happening while the participant is under anesthesia will be in place during and after the procedure, and participant's breathing and other vital signs will be carefully monitored. If participant experience any symptoms other than those that the study doctor has informed the participant are associated with the procedure, please let the study doctor know. Pregnancy Insufficient information is available on the use of Proflavine in pregnancy. Drugs can have harmful effects on the fetus at any stage of pregnancy. Loss of Privacy Subjects will be consented on the day of their procedure. Subjects will be taken to a private area where the study information will be discussed. No additional sensitive information will be requested from the subjects beyond what is required to perform a standard endoscopy. Subjects will be given an ID number for all forms, images, and communications. All data will be removed of identifiers and coded. Source documents will be redacted of all PHI before being sent from outside sites for data monitoring/data entry in the database. All PHI collected on BCM subjects will be stored in locked cabinets or password-protected files/computers where only the PI and study coordinator can see the names. All case report forms will use the assigned subject ID. Since the subject participation is only for one visit, there will be limited opportunity for privacy interests to arise between study recruitment and end of the study. The only extra intrusion of privacy will be an additional phone call within 7 days of the procedure to ensure that the subject has not suffered any adverse events. During the follow-up, only the study coordinator and/or the PI will have contact with the subject. Information pertaining to the study will only be discussed with the subject and messages containing identifiers of the subject's participation will not be left on voice-mail messages. The potential risks/discomforts of participating in the provider survey are very minimal. There may be minimal psychological discomfort if participants feel uncomfortable disclosing their knowledge of endoscopy or esophageal cancer screening to project staff. However, we will reinforce that these data are only meant to guide and improve our provider training program, that their answers will be kept anonymous and confidential, and that their completion of the survey will not affect their employment at USP.

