When research is conducted in collaboration with outside entities or organizations, the PI must obtain the necessary approvals from those entities. The BCM IRB may request documentation that such approvals have been obtained. Please list and describe the planned sites for this multi-site research for which the BCM PI is either Sponsor-Investigator and/or Coordinating Center. Sites that do not meet the requirements for inclusion in section A6a of the protocol summary and BCM informed consent documents should be listed here.

University of Sao Paulo, Brazil: All patients will be enrolled from the University of Sao Paulo under Co-PI [name].

Rice University: Rice University will provide the HRME device and be responsible for bioengineering aspects of the study.

Section I: Potential Benefits

Describe potential benefit(s) to be gained by the individual subject as a result of participating in the planned work.

There may not be any benefit to participants from taking part in this research. However, there is a chance that the mar-HRME may detect an area of neoplasia that was not detected by standard of care endoscopy. For physicians and trainees undergoing surveys, there may be no benefit of participation. Providers will become aware of their knowledge about endoscopy and esophageal cancer screening and the way in which they provide screening recommendations to patients and their families.

Describe potential benefit(s) to society of the planned work.

Participation may help future patients with esophageal squamous cell cancer from what is learned in this study.

Do anticipated benefits outweigh potential risks? Discuss the risk-to-benefit ratio.

The incremental risks of HRME added to the SOC white light with Lugol's iodine are minimal. In > 1000 subjects imaged with the HRME to date, we have had NO serious adverse events. No risks related to either the drug (proflavine) or the device have been noted. White light endoscopy is standard of care and all subjects will be undergoing this SOC procedure so ALL patients will be receiving (at minimal) the standard of care. For the provider surveys, considering the opportunity to improve understanding of endoscopy and esophageal screening and the minimal risks associated with participation, we believe the benefits overwhelmingly outweigh the risks.

Section J: Consent Procedures

J1. Waiver of Consent

Will any portion of this research require a waiver of consent and authorization?

No

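### The adverse-event recording rule covers only the period after the procedure, by phone, and does not say where allergic or blood-pressure events during the procedure are recorded

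*Combined protocol and SAP*

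**What the plan says.** The recording rule is one sentence in F2: "All patient adverse events (bleeding, infection, perforation) that occur within 7 days after the procedure will be recorded on follow up call". It sets a list of events, a time window and a method of collection.

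H1 describes the risks. On the contrast agent: "There is the possibility of a severe allergic reaction to the Proflavine contrast dye", with breathing difficulty and a drop in blood pressure as its signs. On treatment of that reaction: "There are procedures in place to treat participant in endoscopy room in the event that this happens". On sedation: "There may be additional risks from the added time of additional sedation, such as decreased blood pressure". On the endoscopy: "Aspiration (inhaling) of fluid into the lungs during endoscopy This might cause inflammation in the lungs". H1 adds that "participant's breathing and other vital signs will be carefully monitored".

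Other places are wider or point elsewhere. H1 describes the follow-up call as a check for adverse events of any kind and asks participants to report every side effect. H2 requires a Data and Safety Monitoring Plan as an attachment in Section S. H3 gives an external monitor a role in adverse-event monitoring, with access to the digital CRFs. Section K assigns data and safety monitoring to the study statistician. Section E1 classes the study as greater than minimal risk without prospect of direct benefit, and F2 states that proflavine is used under an IND.

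**The concern.** F2 is the instruction that a site would follow when filling in study records. Its three named events are bleeding, infection and perforation. The two risks that H1 attributes to what the research adds are different in kind and in timing: they are acute, and they are expected mainly while the subject is sedated.

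A site that applied F2 literally could manage an allergic reaction or a drop in blood pressure in the room, see the subject recover, and have no instruction to enter it as a study adverse event. The safety record for an IND agent would then be least complete for the events most plausibly caused by that agent and by the longer sedation. Such events are also hard to reconstruct if they are not written down at the time.

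**Working it through.** There is no figure to reproduce; the point rests on comparing the sections.

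**1. Events named.** F2 names bleeding, infection and perforation. H1 ties allergic reaction to proflavine, and decreased blood pressure to added sedation time. Neither appears in the F2 bracket. H1 also lists aspiration, but ties it to endoscopy under anesthesia, not to proflavine or to the extra sedation. The clear mismatches are therefore two.

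**2. Is the list closed?** F2 opens by referring to all adverse events, so the bracket can be read either as a closed list or as examples. H1's wider description of the same call favors examples. On that reading the mismatch of names disappears, and only the window and the method remain at issue.

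**3. Window.** F2 counts the 7 days after the procedure. Recovery falls inside that window. The procedure itself does not. H1 places treatment of an allergic reaction in the endoscopy room, and links the blood-pressure risk to time under sedation. Both therefore belong mainly to the part that the window leaves out.

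**4. Method.** F2 states that subjects receive IV sedation. A subject may never learn of a transient fall in blood pressure that staff corrected, and so cannot be relied on to report it by phone days later. The same limit applies to H1's request that participants report side effects.

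**5. Is there another route into the data?** The items that F1 and F2 record during the procedure are lesion locations, images, reads, confidence, plans, procedure times and biopsy positions. H1's sentence on vital signs describes monitoring, not data entry. The external monitor and the statistician can review only what has been entered. G2 contains no safety summary. The Section S plan and the CRFs were not available, so whether they provide a route is unknown.

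**6. Extent.** The design is single-arm and all 50 subjects receive proflavine and marHRME imaging, so the gap applies to every subject. Its length per subject runs from first proflavine application to the end of the procedure, which the protocol does not state. Section J2 puts the time added by marHRME at 4 to 6 minutes.

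**The case against.** The strongest reply is that this is a wording gap, not a failure to collect safety data. F2 says all adverse events, and H1 describes the call without any list. Staff would know of a reaction that they had treated, and H1 says that follow-up contact is made by the coordinator or the principal investigator, so the subject need not be the only source. Section L covers the cost of events caused by proflavine or the device, which presupposes that they are identified. The Section S plan may set out in-room recording in full.

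Much of this stands, and it rules out several stronger readings that a reader might infer:

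- That none of the H1 risks is captured. The documents do not support this: the call could pick up some of these events, especially delayed ones, and the Section S plan was not seen.
- That nothing is recorded until discharge. Recovery is after the procedure and so inside the F2 window.
- That aspiration is a third intervention-related risk left out. H1 does not tie it to the intervention, and lung inflammation after aspiration could still be apparent within 7 days.
- That the rule would produce a false safety conclusion, or that a zero-event bound on 50 subjects measures the harm. G2 plans no safety endpoint or conclusion. The statement in Section I that "No risks related to either the drug (proflavine) or the device have been noted" reports experience in more than 1000 earlier subjects, not a result of this rule.

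What the reply does not remove is the window and the method. H1's wider wording broadens the kinds of event that the call covers, not its timing or its source. Staff knowledge of an event does not put it in the study record unless an instruction says so.

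**Conclusion.** The concern holds as a gap in the recording rule. F2 as written covers the period after the procedure and relies on a phone call, while the two physical risks that H1 ties to the research intervention would arise mainly during the procedure, under sedation. No section of the reviewed text says that they are recorded as study data.

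The gap applies to all 50 subjects and is limited to the procedure itself. How many events it would lose cannot be estimated, because the documents give no expected rate for either risk. It does not touch the primary accuracy analysis.

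The conclusion assumes that allergic and blood-pressure events occur mainly in the room, as H1's own description implies, and that F2 is the operative rule. If the Section S plan already requires in-room recording, what remains is that F2 should be made to agree with it. This is a correction worth making before enrollment, or at once if enrollment has begun; it is not a fatal flaw.

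**What to change.** Reconcile F2 with H1 by replacing the recording sentence with a rule that says:

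- all adverse events from first proflavine application to day 7 are recorded;
- bleeding, infection and perforation are examples, not a closed list;
- staff enter events during the procedure and recovery, including allergic reaction, hypotension and aspiration, on the procedure CRF before discharge;
- later events are recorded on the follow-up call.

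Align the Section S plan with the same wording. The change concerns recording only and leaves clinical management as it is.

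The cost is an amended F2 sentence, a short adverse-event block on the procedure CRF and a few minutes per case. The reported adverse-event count may rise, because events that would have gone unrecorded are now entered.

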This is a single-arm feasibility study and the clinical procedure will not be performed at Baylor. Baylor is coordinating center and will receive the data and monitor/coordinate the study. The actual feasibility study (n=50) will be conducted at the University of Sao Paolo, Brazil under the local PI, [name]. [name] (Baylor) is the coordinating PI for the overall grant though this pilot project will occur solely in Brazil.

Baylor will travel to USP to initiate the study and provide training on data collection, use and storage of the drug and device, and study procedures. Baylor will oversee the initiation of the feasibility study and the first 25 cases to ensure valid data collection. Baylor will communicate monthly (or more often as needed) with USP research team to answer questions and monitor data collection procedures. Baylor will travel yearly to monitor progress and at the end of the study close-out procedures.

Patients undergoing endoscopy for ESCN screening (n=50) at USP will be recruited by [name] and his team for the study. All study subjects will receive White Light Imaging and Lugol's Chromoendoscopy (LCE) which is the current standard of care procedure. We will record any LCE abnormal (suspicious) areas and record the clinician's plan of action (Biopsy vs. No Biopsy vs. Treat). Following LCE, all subjects will receive Mobile, Augmented Reality High Resolution Microendoscope (marHRME) imaging with the study contrast agent (Proflavine) of any LCE-identified abnormal areas as well as LCE normal areas (1:4 ratio abnormal to normal). We will record the subjective clinician read and confidence level in their diagnosis (high, low), and their plan of action (Biopsy vs. No Biopsy vs. Treat). Then we will image the same abnormal and normal areas with the marHRME and record the software read, clinician confidence level, and plan of action. Finally, the imaged areas will be biopsied or resected and evaluated by a pathologist. All subjects will receive both standard of care and marHRME imaging.

Once data is collected at USP, data will be removed of identifiers and coded and will be transferred to BCM. BCM will be responsible for data entry, management, and analysis.

Inclusion Criteria:

Outpatients undergoing routine (standard of care) Lugol's chromoendoscopic screening for squamous cell neoplasia will be eligible for enrollment including patients with known history of head/neck squamous cell cancer.

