Patients must be >18 years old and able to give informed consent.

For the provider surveys and interviews, all providers (clinicians, trainees) who are working on the project will be eligible to participate. There is no obligation to participate in the study and this will be explained via the research letter included in Section S.

Exclusion Criteria:

- Allergy or prior reaction to the fluorescent contrast agent proflavine - Patients who are unable to give informed consent - known advanced squamous cell carcinoma of the distal esophagus, or dysplastic/suspected malignant esophageal lesion greater than or equal to 2cm in size not amenable to endoscopic therapy - Patient unable to undergo routine endoscopy with biopsy: - women who are pregnant or breastfeeding - prothrombin time greater than 50% of control; PTT greater than 50 sec, or INR greater than 2.0 - inability to tolerate sedated upper endoscopy due to cardio-pulmonary instability or other significant medical issues

For the provider surveys and interviews, all providers (clinicians, trainees) who are working on the project will be eligible to participate. There is no obligation to participate in the study and this will be explained via the research letter included in Section S. Providers will be excluded if they decline participation or otherwise opt out of the proposed research project.

F2. Procedure

[name] will accrue subjects (n=50) already scheduled for endoscopic screening due to a high risk for ESCC (head and neck cancer history; heavy smoking and alcohol, other dietary or geographic risk factors). Lugol's chromoendoscopy (LCE) is the current standard of care for esophageal cancer screening.

To uphold this standard of care and recruit patients already scheduled for endoscopy, LCE will be performed on all patients, followed by marHRME of Lugol's voiding (unstained areas). Subjects will be sedated per standard protocol (IV sedation) and undergo white-light endoscopy with application of Lugol's iodine. In each subject, the location of each Lugol's unstained area (level, quadrant) will be recorded and digital images obtained. The endoscopist's clinical impression will be recorded for each Lugol's abnormal area and visible lesions ('non-neoplastic' vs. 'neoplastic') as well as his/her proposed plan: a. no biopsy, b. biopsy, c. endoscopic treatment.

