However, since Lugol's is used as an initial screen (and is the gold standard for initial screening), only Lugol's abnormal areas will be biopsied so no extra biopsies will be obtained and no additional costs incurred.

All patients participating in the feasibility study will be invited to participate in a brief (20 min) interviewer-administered survey prior to undergoing endoscopy to assess attitudes and barriers to marHRME (T1), and a follow-up interview (7 days post-procedure) to determine experiences and acceptability (T2). Informed consent and the initial interview will be conducted in a private clinic room by trained study staff from the Brazilian team using a brief Portuguese-language survey. The follow-up interview will occur by phone, after a routine follow-up call by clinical staff.

The endoscopists and trainees participating in the feasibility study will be invited to participate in a series of questionnaires and in-depth interviews administered at different time points of the study. Informed consent will be obtained prior to the first interview. Clinicians will answer a brief questionnaire to assess acceptance of marHRME prior to undergoing study training (T1), after training (T2), and after conducting 25 procedures (T3). Providers will be trained on use of the marHRME and review standard endoscopy procedures. Training of providers will be done using a cell phone app, a VR simulation of esophageal endoscopy, followed by directed guidance during the first 5 procedures. At T3, endoscopists and trainees will participate in a 30- minute semi-structured interview to assess marHRME experience. The interviews will be audio recorded, professionally transcribed, and translated (Portuguese to English) for coding and analysis.

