Data of accuracy, sensitivity, specificity, positive predictive value (PPV), and negative predictive value (NPV) for each method will be summarized using proportions and 95% confidence intervals, and compared using McNemar's tests. Our primary study endpoint is accuracy. Other exploratory endpoints include: Clinician confidence and clinical impact (decision

plan change: biopsy vs. not biopsy vs. treat) that will be summarized and presented in a cross table of pre/post software read. These parameters between expert and novice endoscopists will also be summarized descriptively. Biopsy saving and diagnostic yield will be calculated and presented with proportions and their 95% confidence intervals. Assuming a 80% response rate, we anticipate that 40 patients will complete the survey. We will describe the prevalence of specific barriers to endoscopy with confidence intervals around the point estimate. Descriptive statistics will be used to identify experiences of participants undergoing marHRME endoscopy. Associations with $p < 0.05$ will be considered statistically significant.

Section H: Potential Risks/Discomforts

H1. Potential Risks/Discomforts

Describe and assess any potential risks/discomforts; (physical, psychological, social, legal, or other) and assess the likelihood and seriousness of such risks:

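### If F2's biopsy rule governs, G2's accuracy, sensitivity, specificity and NPV for LCE and LCE+marHRME hold only among Lugol's-unstained areas and are not screening performance

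*Combined protocol and SAP*

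**What the plan says.** **F1 (Design).** marHRME images "LCE-identified abnormal areas as well as LCE normal areas (1:4 ratio abnormal to normal"). F1 then says: "Finally, the imaged areas will be biopsied or resected and evaluated by a pathologist". On this text, normally stained sites have histology.

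**F2 (Procedure).** The site set is narrower. Imaging: "marHRME will be performed of all Lugol's unstained (abnormal) sites prior to tissue biopsy". Histology: "In all subjects, all Lugol's abnormal areas will be biopsied (to uphold the standard of care"), and, further on, "only Lugol's abnormal areas will be biopsied so no extra biopsies will be obtained". G1's average of 2-3 biopsies per subject fits F2, and so does Section N, which rules out tissue taken for research alone.

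**The LCE result.** F2 also provides for a binary call before marHRME: "The endoscopist's clinical impression will be recorded for each Lugol's abnormal area and visible lesions". The last paragraph of F2 lists a neoplastic/non-neoplastic read made on Lugol's alone as the first of three reads.

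**G2 (Data Analysis).** "Data of accuracy, sensitivity, specificity, positive predictive value (PPV), and negative predictive value (NPV) for each method will be summarized" with 95% confidence intervals and compared by McNemar's tests. Accuracy is the primary endpoint. G2 does not restrict these measures to unstained sites, does not correct for mucosa without histology, and does not say which LCE result is used.

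**The concern.** Under F2 a site enters the analysis only if Lugol's has already flagged it. Neoplasia in normally stained mucosa never reaches a denominator, and neither does benign mucosa that LCE correctly left alone. Sensitivity, specificity and NPV computed on what remains are conditional on being unstained, but G2 gives them the names of unconditional measures.

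Sensitivity and NPV are the figures from which a reader would judge whether marHRME is safe to add to screening, and Objective 1 in Section D speaks of raising the accuracy of Lugol's endoscopy. If the conditional figures are reported without a label, they invite a conclusion about screening that the F2 data cannot support.

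**Working it through.** **1. The plan's own figure.** G1 gives 50 subjects, accuracy 80% vs 45% (d = 0.35), 0.7 discordant pairs (psi) and a two-sided 5% level. McNemar power is Phi[(d x sqrt(n) - 1.96 x sqrt(psi)) / sqrt(psi - d^2)] = Phi[(2.475 - 1.640) / 0.760] = 86.4%. Enumerating the uncorrected test gives 87.0%. The stated 87% reproduces and does not bear on this point.

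**2. Notation.**
- p: share of sites that are neoplastic.
- Se_L: probability that a neoplastic site is unstained.
- Sp_L: probability that a benign site stains normally.
- s and c: sensitivity and specificity of marHRME among unstained sites.
- The sequence is positive when a site is unstained and marHRME calls it neoplastic.

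**3. What F2 yields against the absolute quantity.**
- Sensitivity: absolute Se_L x s, F2 yields s. The ratio is 1/Se_L whatever s is.
- Specificity: absolute 1 - (1 - Sp_L)(1 - c), F2 yields c.
- PPV: identical, because every sequence-positive site is unstained.
- Accuracy difference between methods: both methods are negative on stained sites, so they agree there. The absolute difference is u times the F2 difference, where u = p x Se_L + (1 - p)(1 - Sp_L) is the unstained share of sites.

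**4. Inputs.** G1 gives LCE sensitivity above 95% and specificity below 65%. I use those bounds, read per site, although G1 states no unit. The documents do not give p, s or c. I assume p = 10%, s = 90% and c = 80%.

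**5. Results for the sequence.**

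| Measure | Absolute | Under F2 |
|---|---|---|
| Sensitivity | 0.95 x 0.90 = 85.5% | 90% |
| Specificity | 1 - 0.35 x 0.20 = 93% | 80% |
| PPV | 0.0855/0.1485 = 57.6% | 57.6% |
| NPV | 0.837/0.8515 = 98.3% | 0.252/0.2615 = 96.4% |
| Accuracy | 0.0855 + 0.837 = 92.3% | 0.3375/0.41 = 82.3% |

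Sensitivity over a range of s: at 80% the absolute value is 76.0%, and at 95% it is 90.25%, so the overstatement runs from 4.0 to 4.75 points. If Sp_L were 36.5% (assumed, to show a lower value), absolute specificity would be 1 - 0.635 x 0.20 = 87.3% against the same reported 80%. NPV is usually understated but can reverse: with p = 18%, Sp_L = 36.5% and s = 95% it is 97.6% absolute and 98.0% under F2.

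**6. The primary contrast.** In the base case u = 0.095 + 0.315 = 0.41. If G1's 35-point target is meant among unstained areas, it corresponds to 0.41 x 35 = 14.35 points over all sites. Normally stained mucosa has no natural site count, so this shows the direction and rough scale only.

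**7. Which LCE result.**
- *Recorded read on Lugol's alone.* LCE can be negative at an unstained site, so all its measures can be computed, within unstained areas. Its sensitivity carries the same factor 1/Se_L as the sequence, so the ratio of the two sensitivities is not distorted.
- *Unstained counted as LCE-positive.* There are no LCE-negative sites. LCE sensitivity is 100%, specificity 0%, NPV 0/0, and accuracy equals PPV.

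**The case against.** The strongest reply is that F1 plans histology on normal areas, and Section I allows that marHRME may find neoplasia missed by standard endoscopy. If F1 governs, the defect largely disappears. The 1:4 sampling would still need weighting before the figures described the screened mucosa. This stands, and it makes the point conditional on how F1 and F2 are reconciled.

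A reader might infer something stronger: that LCE will be reported at 100% sensitivity and 0% specificity, and that McNemar's tests of those two measures test a null that is false by construction. That needs unstained to be the LCE-positive call, and no section says so. Biopsying every unstained area is a standard-of-care rule, while F2 separately records a binary read whose accompanying plan may be no biopsy. G1 also fits that reading poorly. With 45% of sites neoplastic and discordance split 0.525/0.175, it would imply marHRME sensitivity of (0.45 - 0.175)/0.45 = 61% and specificity of 0.525/0.55 = 95%, an odd planning assumption. This is suggestive, not conclusive.

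A reader might also infer that marHRME's own sensitivity and specificity are misstated. They are distorted only if the device performs differently on stained and unstained mucosa, which no document shows. Its NPV is affected in any case, because neoplasia is more common among unstained sites.

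Finally, this is a pilot, F2 discloses that Lugol's acts as the initial screen, and the sensitivity error is modest. That limits the consequence. It does not make the labels right, and accuracy is still the powered primary endpoint.

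**Conclusion.** The point holds, conditional on F2. The accuracy, sensitivity, specificity and NPV planned in G2 for LCE and for LCE+marHRME would be quantities among Lugol's-unstained areas presented as if unconditional. The upper limit of 1/0.95 on the sensitivity overstatement rests only on G1's bound, read per site. The 4.5-point example adds the assumed 90%. The 13-point understatement of specificity (80% against 93%) rests on G1's 65% bound and an assumed 80%, and it errs against marHRME. The accuracy contrast scales with the unstained share of sites, which the documents do not give.

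The documents do not support the conclusion that the comparison itself is invalid. Both methods are read on the same sites, so the pairing is sound within unstained areas. Nor do they clearly support a further inference from F2's statement that marHRME non-neoplastic "sites will be considered not tissue-biopsied for purpose of the analysis". Taken literally, that would also empty the marHRME-negative cells, but it may be meant only for counting biopsies saved and yield.

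**What to change.** Reconcile F1 and F2 on which sites are imaged and which have histology. If the F2 site set is confirmed, change G2 as follows.

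1. Label every accuracy measure *among Lugol's-unstained areas*, and state that absolute screening sensitivity, specificity and NPV are not estimated.
2. Name the LCE result used in the analysis. The natural choice is the neoplastic/non-neoplastic read that F2 already records on Lugol's alone.
3. Only if unstained is instead taken as LCE-positive, drop LCE sensitivity, specificity and NPV and their McNemar tests. Report LCE PPV, the share of neoplastic unstained sites that marHRME keeps, and the share of benign unstained sites that it spares. Give each a patient-level interval, since subjects contribute 2-3 biopsies on average.

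The cost is analysis-plan wording, with no added patients, biopsies or procedures. The price is narrower claims about sensitivity and NPV.
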